$$k=2, 3; 4, w = 1, 2, 3, 4; c=0.1, 0.2, 0.5, 1, 2, 4, 8$$

$P_{\text{cut } c, \text{ group } k, \text{ antigen } w}$  is thus the sero-protection rate, defined by cut-point  $c$ , for vaccination group  $k$  when considering the IgG concentration specific to antigen  $w$ .

The statistical alternative hypothesis is thus:

$$H_1: P_{\text{cut } c, \text{ group } k, \text{ antigen } w} \geq P_{\text{cut } c, \text{ group } 1, \text{ antigen } w} - 0.15$$

If  $H_0$  is rejected this indicates non-inferiority for one specific cut point and antigen.

The evaluation will be done by calculation of the unadjusted risk difference ( $P_{c, \text{ group } k, w} - P_{c, \text{ group } 1, w}$ ) with a two-sided 90% CI, corresponding to a one-sided test at the 5% significance level. The CI's will be approximative Newcombe-Wilson intervals. The  $H_0$  is rejected if the CI is fully above the -15% point limit and this therefore corresponds to a one-sided test at a 5% level.

For the observed IgG concentrations the comparison will be done with the same grouping, but using geometric mean concentrations. Here the  $H_0$  can be expressed as:

$$H_0: GMC_{\text{group } k, \text{ antigen } w} < 2/3 * GMC_{\text{group } 1, \text{ antigen } w}$$

$$k=2, 3; 4, w = 1, 2, 3, 4$$

The evaluation will be done by calculation of the GMCR (GMC ratio) with a two-sided multiplicative 90% CI, again corresponding to a one-sided test at the 5% significance level. The CI's will be based on log-normality. The  $H_0$  is rejected if the CI is fully above the GMCR=2/3 limit and this therefore corresponds to a one-sided test at a 5% level.

For the comparison of vaccination groups 1 to 4 with the placebo group 5, the same analysis is applied, but no non-inferiority consideration is applied. Instead, the usual p-values corresponding to superiority testing will be presented together with the estimated differences and a two-sided 90% CI.

Due to the large number of performed tests, these non-inferiority procedures are considered of non- confirmatory nature and no control for multiplicity is applied.

The primary analyses are based on the BIG analysis set and this will form the basis for conclusions. As sensitivity analyses the primary analyses will be repeated on the BPP analysis set.

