## 3 Analysis sets

In this section, the different analysis sets to be used for statistical analysis are presented. Each subject will be classified according to the definitions below at blinded data review meetings. The classification and related decisions will be made by the study team and documented in the minutes from the meeting. The Baby Immunogenicity Set (BIG) and Baby Per Protocol Set (BPP) refer to the babies born to study subjects.

All safety analyses will be performed on the Safety Analysis Set (SAF) and analysed according to the actual treatment received (treatment arms 1 to 5). All Immunological analyses will be performed on the Maternal Immunogenicity Set (MIG) and BIG sets. The primary immunological analysis (i.e., the immunogenicity results at delivery) will also be performed on the BPP set. These analyses will be based on randomised treatment.

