Due to the large number of performed tests, the non-inferiority procedures are considered of non- confirmatory nature and no control for multiplicity is applied. The expected power of many of the comparisons will be quite low, so only descriptive use of results will be considered.

The primary analyses are based on the BIG analysis set. As sensitivity analyses the primary analyses will be repeated on the BPP analysis set and will be repeated on the BIG set restricted to the babies with an evaluable cord blood sample. A further sensitivity analysis will be done on a further subset of the BPP, eliminating biologically implausible data. Examples of such biological implausible data are (non exhaustive list):

- Data from babies born to mothers with a high concentration of antibodies at delivery, where the baby blood at birth shows no or a very low concentration of antibodies, but who show a high concentration of antibodies at later timepoints
- Data from babies born to mothers with a high concentration of antibodies at delivery, where the baby blood shows no or a very low concentration of IgG antibodies, but where IgG1 is detected at the same timepoints, as part of an exploratory analysis

Setting of the elimination of biologically implausible data will be done after review of the initial immunogenicity data output.

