## 4.6 Analysis of immunogenicity (secondary endpoints)

The following secondary immunogenicity endpoints will be evaluated by standard tabulation by vaccination group and relevant time-point(s):

Based on samples collected in the mother (MIG analysis set):

- Concentrations of IgG antibodies specific to the 4 AlpN proteins in maternal blood, pre-dosing, 4 weeks after each vaccination dose and at delivery
- Relative to baseline (pre-dose) concentrations of IgG antibodies specific to the 4 AlpN proteins in maternal blood, pre-dosing, 4 weeks after each vaccination dose and at delivery

The proportions of mothers who achieve a concentration of IgG specific to the 4 AlpN proteins above 0.1, 0.2, 0.5, 1, 2, 4 and 8 µg/mL at delivery

Based on samples collected in the mother (MIG analysis set) and in the baby (BIG analysis set), and as a sensitivity analysis based on subjects part of the BPP and MPP analysis sets. A further sensitivity analysis will be done on the BPP and MPP, in which biologically implausible data will be eliminated. Examples of such biological implausible data are (non exhaustive list):

- Data from babies born to mothers with a high concentration of antibodies at delivery, where the baby blood at birth shows no or a very low concentration of antibodies, but who show a high concentration of antibodies at later timepoints
- Data from babies born to mothers with a high concentration of antibodies at delivery, where the baby blood shows no or a very low concentration of IgG antibodies, but where IgG1 is detected at the same timepoints, as part of an exploratory analysis

Setting of the elimination of biologically implausible data will be done after review of the initial immunogenicity data output.

- The subject level ratios of antibody concentrations between maternal and cord blood at delivery. The ratio of interest is the antibody concentration measured in cord blood over the antibody concentration measured in maternal blood at delivery. The endpoint is derived for the individual mother-child pair.

Based on samples collected in the baby (BIG analysis set):

- Concentrations of IgG antibodies specific to the AlpN proteins in infant blood of each baby at 1 month and 3 months of age:
- The proportions of babies who achieve a concentration of IgG specific to the AlpN proteins above 0.1, 0.2, 0.5, 1, 2, 4 and 8 µg/mL at 1 month and 3 months after birth will be calculated

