## 6 Interim analyses

There will be blinded, sponsor-internal safety reviews conducted on an ongoing basis as well as recurrent reviews by an unblinded DSMB. The function and responsibilities of the DSMB is documented in the DSMB Charter. The DSMB and the attached independent unblinded statistician and programmer will work in a setup completely separated from the blinded study team.

Unblinded analysis of selected endpoints up to (and including) Visit 8 will be performed based on cleaned data. This analysis (summaries and statistical analysis as described in section 4) will include the primary immunological endpoint for IgG antibodies specific to the AlpN proteins in cord blood, the key secondary safety endpoints in all study participants (maternal participants and babies), and the secondary immunological endpoint for IgG antibodies specific to the AlpN proteins in maternal blood. An overview of the considered objectives, endpoints, and relevant visits is given in Table 5 below.

This analysis will be conducted by an unblinded team within the CRO and sponsor. Separate teams within the CRO and the sponsor will remain blinded until the end of the study to ensure further study execution in a blinded manner. Investigators, and further site personal and study participants will remain blinded until the end of the study. Procedures to ensure that blinded and unblinded personnel remain in their roles are described in a ‘firewall’ charter, an extension of the general blinding plan.

As no hypotheses are tested repeatedly and no early stopping of the trial is envisioned, no multiplicity adjustments related to the early analysis are planned.

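### The rule for dropping biologically implausible baby data in a secondary sensitivity analysis has no numeric limits, is set after the results are reviewed, and is not assigned to group-blind staff

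*SAP*

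**What the plan says.** SAP 4.5 bases the primary analysis on the BIG set. It repeats that analysis on the BPP, and it also "will be repeated on the BIG set restricted to the babies with an evaluable cord blood sample". It then adds a further analysis on a subset of the BPP without biologically implausible data. Two examples are given, in a list described as not exhaustive:

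- the mother's antibody at delivery is high, the baby's at birth is absent or very low, and the baby's is high at later visits;
- the mother's antibody is high, the baby's IgG is absent or very low, but IgG1 is detected at the same time in an exploratory analysis.

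No concentration, cord/maternal ratio or per-antigen rule defines *high* or *very low*. On timing, the SAP says: "Setting of the elimination of biologically implausible data will be done after review of the initial immunogenicity data output".

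SAP 4.6 applies the same approach to the cord/maternal ratio: "A further sensitivity analysis will be done on the BPP and MPP, in which biologically implausible data will be eliminated".

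On blinding, SAP 3 says: "Each subject will be classified according to the definitions below at blinded data review meetings". The sets defined there are SAF, MIG, MPP, BSA, BIG and BPP. SAP 6 says of the Visit 8 analysis: "This analysis will be conducted by an unblinded team within the CRO and sponsor". It also says: "Separate teams within the CRO and the sponsor will remain blinded until the end of the study".

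**The concern.** An exclusion rule that is open-ended, has no numbers and is completed after the output is seen can be shaped by the results it is meant to test. The planned immunogenicity summaries are by vaccination group, so the output under review would ordinarily show group differences.

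Both listed examples work in one direction: they remove low baby values and never high ones. Relative to the BPP, such removals raise cord GMCs, the proportions above the cut-points and the cord/maternal ratios. Removal also requires a *high* maternal concentration at delivery, which the regimen can affect. SAP 4.5 itself expects Group 4 to be sub-optimal. Equal removal across groups therefore cannot be taken for granted.

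At stake is the use of this one analysis as a robustness check when the regimen is chosen. A reader could not tell whether the exclusions were made independently of group results.

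**Working it through.** **1. Does the blinded review cover this step?**

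- SAP 3 applies blinded classification to the six sets it defines. The implausible-data subset is not one of them.
- SAP 3.1 says the analysis sets can be determined from information collected up to 72 hours after delivery. The first example needs later infant samples (1 and 3 months, SAP Table 3), and the second needs exploratory IgG1 data.
- SAP 6 keeps both blinded and unblinded teams at the CRO and the sponsor. It assigns the elimination step to neither.

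The SAP therefore contains no requirement of group-blindness for this rule. It does not say that unblinded staff will set the rule either.

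**2. The plan's own figure.** Inputs: 60 per group, equal true rates, 95.65% (22/23) above 1 µg/mL (SAP 2.3.1, Table 4); margin 15 points and two-sided 90% Newcombe-Wilson interval (SAP 4.5), so z = 1.645. For proportions p_k and p_1, with Wilson lower limit l_k and Wilson upper limit u_1:

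lower limit = (p_k − p_1) − √[(p_k − l_k)² + (u_1 − p_1)²]

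Exact binomial enumeration gives a 96.7% chance that this limit exceeds −15 points. The stated power of above 90% is reproduced.

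**3. Single tables.** For 53/60 vs 57/60: l_k = 0.7981, u_1 = 0.9798, so −0.0667 − √(0.0852² + 0.0298²) = −0.157. The other tables follow in the same way.

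| Group k | Group 1 | Lower limit (points) |
|---|---|---|
| 53/60 | 57/60 | −15.70 |
| 53/59 | 57/60 | −14.00 |
| 53/59 | 57/59 | −15.39 |
| 57/60 | 57/60 | −7.49 |
| 57/60 | 57/59 | −8.84 |
| 57/60 | 57/58 | −10.27 |
| 57/60 | 57/57 | −11.87 |

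One removal from Group k turns 53/60 vs 57/60 from not shown to shown. One removal from each group leaves it not shown. With 57/60 in both groups, removing all three low Group 1 babies still leaves the limit above −15.

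**4. How often would one removal matter?** Same enumeration, 60 per group and equal true rates, at the rates below 100% in SAP Table 4. One baby below the cut-point is removed wherever one exists. Figures are % of trials, per comparison.

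| True rate | Shown, no removal | Becomes shown (removal in Group k only) | Becomes not shown (removal in Group 1 only) | Any change (one removal from each) |
|---|---|---|---|---|
| 95.65 | 96.7 | 2.2 | 2.3 | 1.3 |
| 91.30 | 86.9 | 5.2 | 6.5 | 1.2 |
| 86.96 | 77.7 | 5.8 | 7.5 | 0.1 |
| 82.61 | 70.7 | 5.4 | 7.7 | 0.0 |
| 73.91 | 60.4 | 5.7 | 6.1 | 0.0 |
| 60.87 | 53.8 | 3.2 | 7.0 | 0.0 |

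The last column includes trials in which one group has no baby to remove. Counting only trials where both groups lose one, it is 0.8% at 95.65% and 1.1% at 91.30%. The one-removal figures are upper bounds, because not every baby below a cut-point would meet the rule.

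**5. GMC.** Assume an arm GMC of 10 µg/mL over 60 babies and one removed baby at concentration c. The log shift is (1/59) × ln(10/c).

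- c = 0.1: exp(0.078) = 1.08, or 0.078/0.405 = 19% of the margin ln 1.5.
- c = 0.5: exp(0.051) = 1.05, or 13% of the margin.

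Several removals from one arm would weigh more. In a simulation with equal true GMCs, two comparator babies were placed 100-fold low. Removing them raised the chance of meeting the 2/3 margin from 37% to 86% if the SD of ln IgG is 0.8, and from 20% to 43% if it is 1.5. The documents give no SD, so that range is assumed. By construction these removals correct true errors; the simulation shows leverage, not bias.

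**The case against.** The strongest reply is that almost nothing rests on this analysis. It is a subset of a sensitivity set. The BIG, full BPP and cord-only analyses do not use the rule. Protocol 7.8 says: "The primary analyses are based on the BIG analysis set and this will form the basis for conclusions". SAP 4.5 adds: "The expected power of many of the comparisons will be quite low, so only descriptive use of results will be considered". The full BPP result can be read beside the reduced one. All of this stands and is why the point is minor.

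The early analysis that informs regimen selection stops at Visit 8, whereas the first example needs later infant samples and the second needs exploratory IgG1 data. Removals of the listed kinds may therefore hardly enter that analysis. This also stands, though the list is open and could admit other kinds.

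The blinding gap is an absence of text. SAP 6 refers to a firewall charter that was not available for this review, and it could assign the step. As SAP 6 describes it, however, that charter keeps personnel in their roles; it is not said to decide who sets this rule.

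Both examples require corroboration, so some removals may rightly correct sample or assay errors, and the SAP is open about the timing. That justifies doing the analysis. It does not justify fixing the limits only after the output has been reviewed.

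Finally, the flip rates assume equal true rates, which the plan expects for Groups 1 to 3 only. They do not describe Group 4 vs Group 1.

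**Conclusion.** The concern holds and is minor. The rule has no numeric limits, is completed after review of the output, and is not reserved for group-blind staff. Exclusions of the listed kind move results upward relative to the BPP and bias a between-group comparison only if they fall unequally.

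For one removal from one group, the non-inferiority reading changes in about 2% of trials at the planned 95.65% rate and in 3.2% to 7.7% at the lower Table 4 rates. With one from each group the figure is at most 1.3%. One removal shifts a GMC by a factor of 1.05 to 1.08. Only results near the margin are affected.

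The removal counts and concentrations are assumptions, since the documents give no removal rate. Sixty per group is a maximum, because the set is a subset of the BPP. The primary conclusions are untouched.

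**What to change.** Before any group-level immunogenicity output is released:

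- write numeric definitions of *high* and *very low* into SAP 4.5 and 4.6, and keep the requirement for corroboration from later samples or IgG1;
- state that group-blind staff apply the rule, including to the later infant and IgG1 data;
- report the exclusions by group, with reasons, next to the full BPP result;
- label any criterion added afterwards as post hoc.

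The cost is SAP wording and one group-blind review step, which the blinded teams already kept under SAP 6 could carry out. The small downside is that an unforeseen kind of sample error could then be handled only as a post hoc exclusion.

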## 4.6 Analysis of immunogenicity (secondary endpoints)

The following secondary immunogenicity endpoints will be evaluated by standard tabulation by vaccination group and relevant time-point(s):

Based on samples collected in the mother (MIG analysis set):

- Concentrations of IgG antibodies specific to the 4 AlpN proteins in maternal blood, pre-dosing, 4 weeks after each vaccination dose and at delivery
- Relative to baseline (pre-dose) concentrations of IgG antibodies specific to the 4 AlpN proteins in maternal blood, pre-dosing, 4 weeks after each vaccination dose and at delivery

The proportions of mothers who achieve a concentration of IgG specific to the 4 AlpN proteins above 0.1, 0.2, 0.5, 1, 2, 4 and 8 µg/mL at delivery

Based on samples collected in the mother (MIG analysis set) and in the baby (BIG analysis set), and as a sensitivity analysis based on subjects part of the BPP and MPP analysis sets. A further sensitivity analysis will be done on the BPP and MPP, in which biologically implausible data will be eliminated. Examples of such biological implausible data are (non exhaustive list):

- Data from babies born to mothers with a high concentration of antibodies at delivery, where the baby blood at birth shows no or a very low concentration of antibodies, but who show a high concentration of antibodies at later timepoints
- Data from babies born to mothers with a high concentration of antibodies at delivery, where the baby blood shows no or a very low concentration of IgG antibodies, but where IgG1 is detected at the same timepoints, as part of an exploratory analysis

Setting of the elimination of biologically implausible data will be done after review of the initial immunogenicity data output.

- The subject level ratios of antibody concentrations between maternal and cord blood at delivery. The ratio of interest is the antibody concentration measured in cord blood over the antibody concentration measured in maternal blood at delivery. The endpoint is derived for the individual mother-child pair.

Based on samples collected in the baby (BIG analysis set):

- Concentrations of IgG antibodies specific to the AlpN proteins in infant blood of each baby at 1 month and 3 months of age:
- The proportions of babies who achieve a concentration of IgG specific to the AlpN proteins above 0.1, 0.2, 0.5, 1, 2, 4 and 8 µg/mL at 1 month and 3 months after birth will be calculated

For treatment groups 1 to 4, in a joint analysis, the maternal IgG concentrations from pre-dosing to delivery will be analysed using a log-normal model with repeated measurements within subject, vaccination group and visit as factors and a visit \* group interaction.

An unstructured covariance structure will be implemented for repeated measurements. In case of estimation issues, an auto-regressive AR(1) covariance structure will be used instead to model the correlations within-subject. The Satterthwaite approximation will be used to estimate denominator degrees of freedom and adjust standard errors.

Pseudo code related to the implementation of this model:

```
proc mixed data = IgG data;  
  class subject group visit region;  
  model change_log_titre = baseline region group*visit / ddfm=sat;  
  repeated visit / subject=subject type=UN;  
  lsmeans group*visit / diff cl obsmargins;  
run;
```

Here *change\_log\_titre* is the change from baseline in log(titre), *baseline* is the log(titre) at baseline and *visit* is the study Visit (i.e., 3, 5, 7, 8).

Least square mean estimates of change from baseline in log(titre) with 95% confidence intervals (CI) will be presented after applying the inverse transformation at each time-point for each treatment group.

Estimated group differences at Visit 7 and 8 (when vaccination schedule has been completed) between vaccination groups along with associated 95% confidence intervals and p-values will be presented.

Estimated least square means and associated 95% CI of change from baseline in log(titre) will be plotted over time by treatment group.

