## 7.9 Analysis of immunogenicity (secondary endpoints)

The following secondary immunogenicity endpoints will be evaluated by standard tabulation by vaccination group and relevant time-point(s):

Based on samples collected in the mother (MIG analysis set):

- Concentrations of IgG antibodies specific to the 4 AlpN proteins in maternal blood, pre-dosing, 4 weeks after each vaccination dose and at delivery
- Relative to baseline (pre-dose) concentrations of IgG antibodies specific to the 4 AlpN proteins in maternal blood, pre-dosing, 4 weeks after each vaccination dose and at delivery
- The proportions of mothers who achieve a concentration of IgG specific to the 4 AlpN proteins above 0.1, 0.2, 0.5, 1, 2, 4 and 8 µg/mL at delivery
- The subject level ratios of antibody concentrations between maternal and cord blood at delivery

Based on samples collected in the baby (BIG analysis set):

- Concentrations of IgG antibodies specific to the AlpN proteins in infant blood of each baby at 1 month and 3 months of age:
- The proportions of babies who achieve a concentration of IgG specific to the AlpN proteins above 0.1, 0.2, 0.5, 1, 2, 4 and 8 µg/mL at 1 month and 3 months after birth will be calculated

For treatment groups 1 to 4, in a joint analysis, the maternal IgG concentrations from pre-dosing to delivery will be analysed using a log-normal model with repeated measurements within subject, vaccination group and visit as factors. Possibly allowing for changing variance across visits and visit times group interaction. In this way the ratio of GMCs (GMCR) comparing vaccination groups can be derived.

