## 4 Statistical analyses and presentation of data

### 4.1 General considerations and summary of analyses

Summary tables presenting immunogenicity data (mothers and babies alike) as well as AEs including solicited injection site events and systemic AEs following the vaccinations will be presented a) pooled across all countries/sites and b) by geographical location South Africa / Europe (DK+UK).

All data collected from all sites will be sent to and analysed at Larix. Unless otherwise specified, all statistical tests will be performed using a two-sided test at a 5% significance level. Results from analyses will be presented with estimates, 95% confidence intervals (CIs) and p-values. For log-transformed analyses, which might be relevant for immunogenicity endpoints, the anti-log transformation will be applied before presentation. These transformed data will also be tabulated by geometric mean and coefficient of variation. Exposure to vaccinations and compliance with the vaccination schedule will be tabulated and listed.

Numerical/continuous data will be presented in summary tables by number of subjects, arithmetic mean (geometric mean and coefficient of variation [CV] where applicable), median, standard deviation (SD), minimum and maximum (or range). Categorical data will be presented by frequency and percent of subjects as well as number of events, where applicable. All data will be listed (see section 9, Layout of the outputs), and all endpoint data will be tabulated.

As there are more than one observation per subject (both mothers and babies) over time, time-dependent visualizations and, if possible, corresponding time-dependent statistical tests and modelling are carried out.

Prior and concomitant medication will be coded after WHO Drug Dictionary. Medical history and adverse events will be coded using the latest available version of MedDRA.

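### The maternal IgG model shares one covariance matrix across Groups 1–4, so its per-arm Visit 3 intervals may be mis-sized

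*SAP*

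**What the plan says.** SAP 4.6 analyses change from baseline in log titre at Visits 3, 5, 7 and 8, for Groups 1–4 jointly. Group 5 is not in the model. The fixed effects are one baseline slope, region, and a separate mean for each group at each visit.

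On covariance the text says "An unstructured covariance structure will be implemented for repeated measurements", and the code reads "repeated visit / subject=subject type=UN". Neither makes the matrix specific to an arm. The fallback is shared across arms as well: "In case of estimation issues, an auto-regressive AR(1) covariance structure will be used instead".

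The outputs include per-arm intervals at each time-point: "Least square mean estimates of change from baseline in log(titre) with 95% confidence intervals (CI) will be presented". They are also drawn: "Estimated least square means and associated 95% CI of change from baseline in log(titre) will be plotted over time by treatment group". Between-arm differences are reported only for Visits 7 and 8.

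Protocol 7.9 is looser about the model: "Possibly allowing for changing variance across visits and visit times group interaction".

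Outside the model, SAP 4.1 adds summary tables: "These transformed data will also be tabulated by geometric mean and coefficient of variation". SAP 4.5 specifies a per-arm GMC with a 95% interval for cord blood. No equivalent arm-specific interval is specified for maternal blood.

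**The concern.** The Visit 3 sample is drawn before the second injection (Protocol 4.3.2). By the allocation in SAP Table 1, Groups 2 and 3 have then had one vaccine dose and Groups 1 and 4 only saline. The model lets the means differ between these arms but gives all four the same Visit 3 variance.

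If women vary more in log change after a vaccine dose than after saline, the pooled variance lies between the two true values. The interval for the first-dose response at 22 weeks in Groups 2 and 3 would then look more precise than it is, and the saline arms would look noisier than they are. These are the only per-arm intervals that the SAP spells out for maternal IgG, and IgG at 4 weeks after each dose is a stated secondary objective.

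**Working it through.** The plan gives no figure for this model, so there is none to reproduce.

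**Inputs.** From the documents: two vaccinated arms (Groups 2, 3) and two saline-to-date arms (Groups 1, 4) at Visit 3, with 60 women each. Assumed: r, the SD of log change after saline divided by that after vaccine. The documents give no such SD, so r runs from 0.1 to 0.8, with r = 1 as the no-effect case.

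**Closed form, no covariates.** With equal arm sizes, the pooled SD relative to the vaccine SD is k = √((1 + r²)/2).

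- Groups 2 and 3: interval width is k times the correct width; coverage is 2Φ(1.96k) − 1.
- Groups 1 and 4: interval width is k/r times the correct width; coverage is 2Φ(1.96k/r) − 1.

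| r | k | Groups 2/3 coverage | Groups 1/4 width ratio | Groups 1/4 coverage |
|---|---|---|---|---|
| 0.1 | 0.711 | 83.6% | 7.11 | 100% |
| 0.3 | 0.738 | 85.2% | 2.46 | 100% |
| 0.5 | 0.791 | 87.9% | 1.58 | 99.8% |
| 0.8 | 0.906 | 92.4% | 1.13 | 97.3% |
| 1 | 1 | 95.0% | 1 | 95.0% |

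Example for r = 0.3: k = √(1.09/2) = 0.738; 1.96 × 0.738 = 1.447; 2Φ(1.447) − 1 = 85.2%.

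**On the fold scale.** Take assumed natural-log SDs of 1.0 (vaccine) and 0.3 (saline), with n = 60. The correct half-width is exp(1.96 × 1.0/√60) = 1.29-fold in Groups 2 and 3 and exp(1.96 × 0.3/√60) = 1.08-fold in Groups 1 and 4. The pooled model gives exp(1.96 × 0.738/√60) = 1.21-fold to all four.

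**With the baseline term.** Simulating the planned model with its single baseline slope at r = 0.3 gave about 82–90% coverage in Groups 2 and 3 and 99–100% in Groups 1 and 4 across assumed slopes.

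**Visits 7 and 8.** When only the Visit 3 spread differed, simulated per-arm coverage at the later visits stayed close to 95%. Suppose instead that single-dose Group 4 has SD s at those visits and the other arms have 1. The ratio of model SE to true SE is √((3 + s²)/(2(1 + s²))) for Group 4 versus 1 and √((3 + s²)/4) for Group 2 versus 1. For s = 0.7 these are 1.082 and 0.934, giving coverage of 96.6% and 93.3%. For s = 1.3 they are 0.934 and 1.083, giving 93.3% and 96.6%. At s = 1 both are 95%.

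**Effect of a by-arm matrix alone.** The model has one baseline slope for every arm and visit. With `group=group` on the REPEATED statement, low-variance saline cells dominate its estimate. Assumptions for the check: 60 per arm, complete data, correlation 0.6, baseline and vaccine-arm residual SD both 1, r = 0.3, and slope 0 after saline.

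- Vaccine slope −0.5: the fitted slope moves from about −0.34 to about zero, and the Visit 8 SE for Group 2 versus 1 rises from about 0.185 to 0.206 (0.206/0.185 = 1.11).
- Vaccine slope −0.8: SE rises from about 0.186 to between 0.230 and 0.238 (ratios 1.24 to 1.28).
- Vaccine slope −0.3: about 4% wider. Slope 0: no change.

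With `baseline*group*visit` in place of the single slope, the Visit 8 SE is about 0.183–0.184 and Visit 3 coverage about 94–96%.

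**Table 5.** It gives Visits 1, 4, 6 and 7 for the endpoint at 4 weeks after each dose. The visit descriptions in Protocol 4.3.2 take maternal immunogenicity samples at Visits 1, 3, 5, 7 and 8, which matches the five in Protocol Table 4. Visits 4 and 6 have none.

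**The case against.** The strongest reply is that a common unstructured matrix is a conventional default and consistent with the protocol. Protocol 7.9 mentions variance changing across visits, not across arms, and the unstructured matrix allows exactly that. This stands: the SAP does not depart from the protocol.

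Second, the size rests wholly on assumed SDs. This also stands. The 7.11-fold widening needs r = 0.1, which nothing in the documents supports or excludes.

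Third, a reader with an arm's geometric mean, CV and n can build an arm-specific interval. That is true, but the interval displayed would still be the pooled one.

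Fourth, the obvious repair, a by-arm matrix on its own, can damage the Visit 7 and 8 differences, which are the only contrasts reported with p-values. The calculation above bears this out, so it should not be adopted alone.

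A reader might go further and infer that regimen selection is at risk, since maternal IgG is part of the early analysis. The documents do not support that: Protocol 2.5 rests selection on cord-blood IgG and safety, and no test or stated decision uses the Visit 3 intervals. Nor does Table 5 imply a wrong analysis. There are no samples at Visits 4 and 6 to analyse, and SAP 6 refers the early analysis back to section 4.

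**Conclusion.** The point holds as a conditional and limited one. If the SD of log change at Visit 3 is smaller after saline than after vaccine, the model-based per-arm intervals at that visit are too narrow in Groups 2 and 3 and too wide in Groups 1 and 4. Over assumed ratios of 0.1 to 0.8, coverage in Groups 2 and 3 is about 84–92% without covariates; with the baseline term it is about 82–90% at a ratio of 0.3. With equal SDs nothing is wrong. Satterthwaite degrees of freedom do not correct a variance wrongly shared between arms.

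What is affected is secondary and descriptive: the presented Visit 3 intervals and the plotted error bars. The cord-blood primary analysis and the arm-specific tabulations are untouched. It would be too strong to say that the Visit 7 and 8 differences are mis-sized. They are sound if arm variances are similar at those visits, and an assumed Group 4 SD of 0.7 to 1.3 times the others moves coverage by less than 2 points. The Table 5 slip is editorial and adds no weight.

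**What to change.** **Preferred.** Keep the planned common unstructured model for the Visit 7 and 8 differences. State in SAP 4.6 that the presented and plotted per-arm Visit 3 intervals come from each arm's own SD of log change: mean log change ± t × SD/√n, back-transformed. This costs a sentence and a little extra programming. The Visit 3 intervals would not be adjusted for baseline or region, so they should be centred on the arm's own mean and footnoted. They would also no longer depend on whether the AR(1) fallback is used.

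**Alternative.** Use `group=group` on the REPEATED statement, but only together with `baseline*group*visit` in place of the single baseline slope. Covariance parameters rise from 10 to 4 × 10 = 40 and baseline slopes from 1 to 4 × 4 = 16, so non-convergence is more likely. The SAP should say in advance that the preferred option applies if the model does not converge. Using `group=group` alone is not recommended: it can widen the Visit 8 between-arm SE by about 11–28% under assumed vaccine-arm slopes of −0.5 to −0.8.

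**Editorial.** In SAP Table 5, list Visits 1, 3, 5 and 7 for the 4-week endpoint, to agree with the sampling schedule and with SAP 4.6.
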